8. PARTICIPANT SAFETY

An adverse event is any untoward medical occurrence in a research subject. An adverse event/reaction is **serious** if it:

results in death is life threatening results in persistent or significant disability/incapacity requires hospitalisation prolongs a current hospitalisation results in a congenital anomaly or birth defect

Adverse events and incidents that may affect the safety of the participants during their attendance at the Assessment Visit will be recorded in the study records and reported to the Sponsor in accordance with University of Bristol policy and procedures.

9. ECONOMIC EVALUATION

The primary economic analysis will provide a preliminary assessment of the incremental NHS care costs of the DRIFT intervention compared to usual care based on data extracted from the hospital records combined with national and local unit cost data, discounted (at standard rates) over time. These data will be supplemented by a more detailed description of the broader impact of DRIFT on use of specialist rehabilitation services, education, informal care and family work patterns for children and their families at age 11. Due to the limited level of detail on quality of life and non-NHS resource use prior to age 11, we plan a cost consequence [18] analysis quantifying NHS resource use over the 11 year period and providing a more detailed snapshot of the broader perspective on economic (e.g. educational, rehabilitation costs, informal care, productivity) and quality of life impact at age 11. This will provide an estimate of whether the initial costs of DRIFT are counterbalanced by lower NHS secondary care costs during the first 11 years of life or lower societal costs and improved quality of life at age 11.

Modelling of long-term costs and outcomes: In secondary economic analysis, we will develop a decision tree and Markov model to estimate the cost-effectiveness (cost per quality adjusted life year [QALY]) of DRIFT compared to standard care from birth to age 18. The primary perspective will be NHS and personal social services in accordance with the NICE methods guide. However, in secondary analysis we will broaden the perspective to include education, parental expenses and lost productivity. The structure of the model will be similar to that outlined by Petrou and Khan using a Markov model to stratify cohorts of surviving children by the degree of disability (none, mild, moderate, severe) with an annual cycle length [13].

Several parameters of the model will be derived directly from DRIFT trial data (i.e. cost of initial inpatient care to discharge and readmissions to age 11; probability of survival to discharge and at yearly intervals to age 11; disability status at age 2 and age 11; other NHS costs, educational, informal care, and productivity costs at age 11; health utilities at age 11. However, other parameters needed to interpolate between birth and age 11 and extrapolate to age 18 will be drawn from the literature or from expert opinion [19], [20]. Distributions will be assigned to all stochastic parameters within the model and a probabilistic sensitivity analysis will be conducted. Deterministic sensitivity analyses will be used to test the impact of various clinically plausible scenarios for the progression of disability beyond age 11. A 3.5% annual discount rate will be used for both costs and benefits. Results of the model will be summarised using incremental cost-effectiveness ratios, the net monetary benefit statistic and cost-effectiveness acceptability curves.

We will use the model to judge the probability that DRIFT is a cost-effective (compared to NICE threshold – currently £20-£30,000 per QALY) at age 11 and age 18. If the evidence is equivocal at age 11, we will use the model to calculate the expected value of sample information [21] to determine the value of further follow up of disability, quality of life and costs beyond age 11.

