After initial feasibility testing showed DRIFT was technically possible and promising, the DRIFT randomised trial started recruiting in 2003. Eligible babies were preterm, had an IVH and expanded the cerebral ventricles over pre-determined limits. With parental consent, 74 babies were randomised in Bristol and Katowice, Poland to either DRIFT or to standard therapy which consisted of non-surgical conventional management (lumbar punctures to control excessive expansion and pressure symptoms). If repeated lumbar punctures were needed, a ventricular reservoir was inserted to facilitate tapping CSF.

Short term outcomes in the DRIFT trial showed no difference in shunt surgery or death. There was a significant increase in secondary bleeding in the DRIFT group. Magnetic resonance (MR) imaging was carried out on clinical indications in 36 of the 50 Bristol survivors.

At 2 years post term, severe disability or death was significantly reduced in the DRIFT group, when neurodevelopment was assessed by "blinded" observers [2]. There was an important decrease in severe cognitive disability (Bayley mental development index 3 SDs below mean) from 59% to 31% (adjusted odds ratio: 0.17 [95% CI 0.05-0.57]) and the difference in median MDI was more than 18 points. Developmental quotient at 2 years correlated significantly with qualitative grading of MR brain images at term. Sensorimotor disability remained substantial at 2 years: overall, 48% were unable to walk, and 20% were unable to communicate. Ventricular enlargement is typically greatest in the occipital areas and 9% of the children had no useful vision. Severe sensorimotor disability was less common in the DRIFT group but without reaching statistical significance.

However, while (relatively) short term neurodevelopmental measures are essential in the initial management of perinatal interventions, longer term measures provide far greater validity in assessing long term functioning (and the medical, societal and financial implications of these).

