5.2 Statistical Considerations

In total 74 children (54 from Bristol and 20 from Poland) were randomised to the DRIFT trial of which 66 survived. 16 children are available for assessment in Poland and 50 in Bristol. Based on a similar effect size documented with severe cognitive disability at 2 years of age a two group continuity corrected chi-square test with a 5% two-sided significance level will have 80% power to detect the difference in severe cognitive disability between a control group proportion of 59% and odds ratio of 0.17 (i.e. an intervention proportion of 19.7%) when the sample size in each group is 28. With 60 infants (30 in each group) we will have 97% power (with an alpha of 5%) to detect a mean cognitive difference of 1 standard deviation (commonly 15 points) between the DRIFT and control groups.

45 UK children will be assessed in Bristol, and 15 Polish children in Katowice, Poland, assuming a 90% follow-up rate. It is intended to recruit 45 Children (22 DRIFT, 23 Control) from the Bristol cohort and 15 (8 DRIFT, 7 Control) from the Poland cohort.

Funding is available for the study to be completed in the UK and in Poland. **This protocol describes the UK cohort only**. The Poland cohort will be completed under a separate protocol and in accordance with local governance and regulatory requirements.

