5.3 Participant Selection

Inclusion Criteria:

- Children previously recruited to the DRIFT trial
- Parents/carers are willing and able to give informed consent and children willing to assent to participation in the study.

Exclusion Criteria

• Children with metal implants that are incompatible in MRI scanners will be excluded from the neuroimaging element of the study.

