6.5 Quality of life, productivity, health, social care and other resource use

The Study Researcher will ask parents to complete the following questionnaires on behalf of their child.

- Two generic preference based measures of the child's health related quality of life: The HUI3, and the EQ-5D-5L proxy versions.
- A modified version of the Client Service Receipt Inventory (CSRI) Children's version [17] to assess parent/carer productivity (completed by both parents/guardians where applicable). The modified CSRI also assesses the child's use of hospital, and community based health services, social and supportive care, educational services in the past 12 months.

The Study Researcher will also extract information on hospital care from the hospital and primary care records since birth to estimate the cost of initial hospitalisation and subsequent readmissions.

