Consent will be sought for the research team to access all the children's health records, routinely collected data and educational outcomes for this study and for future research use (subject to appropriate ethical approval), as well as for linkage of these data in the long term.

Families will be reimbursed for their expenses in taking part. The children will be given a gift voucher (£20) as a small token of thanks for their participation.

It is not intended to give the families individual feedback on full analysis of the assessments and images. A picture of the brain scan will be given to the child and parents if they wish. A summary of relevant findings will be sent in a letter with an offer to discuss them more fully on the telephone or face-to-face.

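### The stated route to hospital records does not reach the 4 of 54 Bristol infants who died, so the primary cost comparison, followed as written, would cover survivors only

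*Protocol*

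**What the plan says.** **The estimate.** Section 9 describes the primary economic analysis as a preliminary assessment of the "incremental NHS care costs of the DRIFT intervention compared to usual care based on data extracted from the hospital records". Section 4.2 lists the cost of the initial hospitalisation, including intensive care, as an outcome for the UK cohort, a term it does not define.

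**The data.** Section 6.5 (quality of life and resource use) has the study researcher "extract information on hospital care from the hospital and primary care records since birth to estimate the cost of initial hospitalisation and subsequent readmissions". This stands among the participant assessments, next to the parent questionnaires, and does not say which children it covers.

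**The access route.** Section 5.3 admits children from the trial provided that "Parents/carers are willing and able to give informed consent and children willing to assent to participation in the study". In section 7.1 the relevant sentence opens "Consent will be sought for the research team to access all the" and goes on to name the children's health records. Consent is taken in person from the parent of a child who is to be assessed. The same section searches NHS and death-registration sources, but only to establish survival status and find current addresses.

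**The model.** Section 9 starts the decision tree and Markov model at birth. Among the inputs to come directly from trial data it lists "cost of initial inpatient care to discharge and readmissions to age 11; probability of survival to discharge and at yearly intervals to age 11".

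**The counts.** Section 5.2: "In total 74 children (54 from Bristol and 20 from Poland) were randomised to the DRIFT trial of which 66 survived", and "16 children are available for assessment in Poland and 50 in Bristol". Section 3.1 reports neonatal MR imaging "in 36 of the 50 Bristol survivors".

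**The concern.** A developmental quotient does not exist for a child who has died, so restricting the cognitive comparison to survivors is at least forced by the outcome. Cost is different. An infant who was randomised and later died still used neonatal care, and in the DRIFT arm may also have had the procedure. Those costs belong to the arm to which the infant was randomised.

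Section 9 asks whether the initial costs of DRIFT are offset by later savings. If the infants who died supply no cost, that question is answered for survivors but reported as the incremental cost of the intervention. Any imbalance in deaths between the arms then moves the answer by an amount the analysis cannot show. The model faces a related mismatch: its survival probabilities describe everyone randomised, while its inpatient costs would come from children alive and taking part some 8 to 11 years later.

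**Working it through.** **1. Reproduce the protocol's counts (section 5.2, checked against section 3.1).**
- Survivors: 50 + 16 = 66, as stated.
- Planned Bristol recruitment: 0.90 × 50 = 45, as stated.
- Deaths: 74 − 66 = 8 overall; Poland 20 − 16 = 4; Bristol 54 − 50 = 4.
- Bristol deaths as a share of those randomised: 4/54 = 7.4%.

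**2. Whom the access route reaches.** Planned participants are 45/54 = 83.3% of the randomised Bristol infants. The other 9 (16.7%) are 4 deaths and 50 − 45 = 5 survivors not expected to take part. The 5 are ordinary non-participation and a separate matter. The 4 cannot enter by the stated route at all.

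**3. Effect on the cost difference.** The protocol gives no cost by arm, so only the form of the shift can be derived. Let each arm have n infants, with d1 deaths in the DRIFT arm and d0 in the control arm. Let G be the mean cost of a survivor minus the mean cost of an infant who died, assumed equal in the two arms. Then

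all-randomised difference − survivors-only difference = −[(d1 − d0)/n] × G.

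With an assumed n = 27 (54/2; Bristol arm sizes are not given) and d1 + d0 = 4:
- 2:2 split: 0.
- 3:1 split: 2/27 = 0.074 × G in absolute size.
- 4:0 split: 4/27 = 0.148 × G in absolute size.

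**4. Which splits are plausible.** Planned recruitment of 22 DRIFT and 23 control at 90% implies 22/0.9 = 24.4 and 23/0.9 = 25.6 survivors. Taken as 24 and 26, with 27 per arm, this is 3 and 1 deaths. It is equally consistent with 25 and 25 (22.5 each, rounded to 22 and 23), which is 2 and 2. A 4:0 split is an outer bound.

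**5. Illustration in pounds, 3:1 split. Every value of G is an assumption.**
- G built only from the age-11 annual cost of a child with serious disability in section 3.1, with no difference in the neonatal stay: 11 × £1,225 = £13,475; 0.074 × £13,475 ≈ £1,000 per child.
- G of £40,000 to £100,000: about £3,000 to £7,400 per child.
- If an infant who died cost more than a survivor, G is negative and the sign reverses. Letting a death cost 0.25 to 2 times the mean survivor cost C, the shift runs from 0.056C one way to 0.074C the other.

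**The case against.** The strongest reply is that the protocol nowhere limits costs to survivors. Section 4.2 speaks of the UK cohort and section 9 of DRIFT trial data, and either could cover all 54. Section 7.1 mentions an existing trial database, which might hold resource use for the infants who died. The mention of surviving children in section 9 concerns only the disability strata of the Markov model. Section 3.1 reports no difference in death between the arms. Defining a costing population is commonly left to an analysis plan, which is not shown.

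Much of this stands. A reader might infer that the protocol excludes the deaths, that their costs are known to have been recorded, or that the model's non-survivor branch has no cost. The documents support none of these. They do not name the children costed or say what the database holds. They do not say whether the four died before or after discharge. Section 9 does not say how non-survivors are costed, and it allows some parameters to come from literature or expert opinion.

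Two things survive the reply. An analysis plan can define a population, but it cannot supply records or an approval that the protocol's access route never reaches. And no reported difference in death, from a trial of 74, does not establish equal numbers among the 54.

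**Conclusion.** The point holds as a gap in data access and in the definition of the costed population. The one stated route to hospital records runs through participating families and misses 4 of 54 Bristol infants (7.4%). Followed as written, it gives a survivors-only cost difference under the name of an incremental cost of DRIFT, and a model that joins survival from birth to inpatient costs from participants.

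The size and direction of any bias are unknown. Assuming 27 per arm and an equal survivor-minus-death cost gap in both arms, the shift is zero for a 2:2 split and 0.074 of the gap for a 3:1 split. A reader might take the pound figures, or the 4:0 bound, as an estimate of bias against or in favour of DRIFT. They are not, since neither the split nor the costs are given. The cognitive primary outcome is not affected.

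**What to change.** - State in section 9 that initial-hospitalisation cost and cumulative NHS cost are compared by randomised arm over all 54 UK infants, with each infant who died costed to the date of death and at zero afterwards.
- Add to section 7.1 the approval needed to use records of deceased participants. Failing that, name the DRIFT trial database as the source of their resource use, if it holds it.
- Use these costs for the non-survivor branch of the decision tree.
- Report the survivors-only difference as secondary.

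The cost is extraction of about four more records, one additional approval and a few sentences. The change does not deal with the roughly five survivors not expected to take part; their missing costs need handling in the analysis plan.

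### The value-of-information calculation for follow-up beyond age 11 is tied to the age-11 verdict, although such follow-up mainly informs the age-18 verdict

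*Protocol*

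**What the plan says.** All the relevant text is in section 9 (Economic Evaluation) of the protocol.

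- The secondary economic analysis models the cost-effectiveness "of DRIFT compared to standard care from birth to age 18".
- Several inputs up to age 11 come directly from trial data, but "other parameters needed to interpolate between birth and age 11 and extrapolate to age 18 will be drawn from the literature or from expert opinion".
- Uncertainty after age 11 is recognised: "Deterministic sensitivity analyses will be used to test the impact of various clinically plausible scenarios for the progression of disability beyond age 11".
- The model will be probabilistic: "Distributions will be assigned to all stochastic parameters within the model and a probabilistic sensitivity analysis will be conducted".
- The probability that DRIFT is cost-effective is judged at two ages, and the condition follows at once: "at age 11 and age 18. If the evidence is equivocal at age 11".
- The calculation that depends on this condition is the EVSI: "If the evidence is equivocal at age 11, we will use the model to calculate the expected value of sample information". Its purpose is "to determine the value of further follow up of disability, quality of life and costs beyond age 11".

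No other trigger for a value-of-information analysis is given, and the age-18 result plays no part in the one that is.

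**The concern.** An EVSI asks how much a decision would be expected to improve if particular data were collected. The data in question here would be gathered after age 11. They would mainly reduce uncertainty about disability, quality of life and costs between 11 and 18, which are the years the model fills from literature and opinion. Their value therefore depends on how uncertain the decision is over the horizon that contains those years. The stated condition looks at the shorter horizon.

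The two verdicts can differ. Section 9 itself asks whether the initial costs of DRIFT are offset later by lower costs and better quality of life, so it foresees costs that come early and benefits that build up. A clear result at 11 with an open one at 18 is a pattern the plan should be ready for. At stake is whether the economic report includes a planned answer on the worth of following this cohort further when that pattern occurs.

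**Working it through.** The protocol states no EVSI, net benefit or probability of cost-effectiveness, so there is no figure to reproduce. The check is of the rule's logic, first from the text and then with a worked illustration.

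**From the text.** Write INB11 for the incremental net benefit to age 11, Y for the increment from 11 to 18, and INB18 = INB11 + Y. Data collected after age 11 mainly inform Y. The age-11 verdict depends on INB11 alone, and the age-18 verdict on INB11 + Y. A condition on INB11 therefore cannot, by itself, show whether learning about Y could change the decision.

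**Illustration.** Every monetary input below is an assumption; none comes from the protocol.

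- INB11 has SD £4,500, Y has SD £8,000, and the two are independent. The SD of INB18 is √(4,500² + 8,000²) = £9,179.
- Follow-up resolves a fraction f of the variance of Y, with f = 0.25, 0.50 or 0.75. The preposterior SD is s = √f × 8,000, which is £4,000, £5,657 or £6,928.
- With a = |mean INB18| / s, the normal unit-loss formula gives EVSI = s × [φ(a) − a × (1 − Φ(a))] per child.

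| Case | Mean INB11 | Mean Y | P at 11 | P at 18 | EVSI (f = 0.25 / 0.50 / 0.75) | Committed to by the rule? |
|---|---|---|---|---|---|---|
| A: decisive at 11, open at 18 | −£10,000 | £10,000 | 0.013 | 0.500 | £1,596 / £2,257 / £2,764 | No |
| B: decisive at 11, uncertain at 18 | £10,000 | −£8,000 | 0.987 | 0.586 | £791 / £1,396 / £1,878 | No |
| C: equivocal at 11, settled at 18 | £0 | £25,000 | 0.500 | 0.997 | about £0 | Yes |
| D: equivocal at both | £0 | £0 | 0.500 | 0.500 | £1,596 / £2,257 / £2,764 | Yes |
| E: decisive at both | £10,000 | £15,000 | 0.987 | 0.997 | about £0 | No |

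P is the probability that DRIFT is cost-effective. Two entries in full, at f = 0.25:

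- Case A: P at 11 = Φ(−10,000 / 4,500) = Φ(−2.22) = 0.013. Mean INB18 = 0, so a = 0 and EVSI = 4,000 × 0.399 = £1,596.
- Case B: mean INB18 = £2,000, so P at 18 = Φ(2,000 / 9,179) = 0.586. Then a = 0.5 and EVSI = 4,000 × (0.352 − 0.5 × 0.309) = £791.

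A and D have opposite age-11 verdicts (decisive and equivocal) and the same EVSI. C and D have the same age-11 verdict, and their EVSIs lie at opposite ends of the table. So the age-11 probability does not determine the EVSI. The rule gives the sensible answer in D and E and the wrong one in A, B and C. The pound figures only show the pattern; they do not estimate this trial's EVSI.

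**The case against.** The strongest reply concerns the reading. The protocol often uses age 11 for the point of data collection, for instance for utilities, family impact and disability status. The condition could then mean all the evidence in hand when this follow-up ends, including the projection to 18, and there would be no mismatch. This reading is possible but not stated, and the sentence just before uses age 11 and age 18 as model horizons. If it is what was meant, the sentence needs the same clarification.

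Three further replies reduce the weight of the point, and they stand:

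- A promise to calculate in one case is not a ban in others. A reader might infer that a decisive age-11 result cancels the EVSI. The text supports only that the plan does not commit to it then.
- The probability of cost-effectiveness at 18, the acceptability curves and the scenarios for disability after 11 are planned unconditionally. A toss-up at 18 would still be visible; only the supplementary statistic might be absent.
- Valuing further research is not among the listed aims in section 4, and the EVSI is a contingent step in a secondary analysis.

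A reader might also infer that the rule fails exactly where the calculation is needed. That is too strong. Uncertainty to age 11 carries into the age-18 result, later data may inform correlated earlier parameters, and the rule works when both verdicts are open or both closed.

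Last, a reader might attach a sum to the rule by multiplying a value of perfect information by the protocol's estimate of about 200 new cases a year. The documents do not support this. The mean and SD of net benefit would be invented, a mean of zero gives the maximum for any SD, and perfect information is only an upper bound on what a sample of about 60 children could yield.

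**Conclusion.** The mismatch holds on the natural reading of section 9. It is a stated rule set at the wrong horizon, not a detail left for an analysis plan. It bites when the two verdicts disagree: decisive at 11 and uncertain at 18 leaves the calculation without a commitment, while equivocal at 11 and settled at 18 commits to one of little value.

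This rests on two premises: that the condition refers to the age-11 model horizon, and that data gathered after age 11 mainly inform the years after it. The primary outcome and the primary economic analysis are untouched. No monetary size can be given from the documents. It is a cheap improvement, not a flaw that threatens the trial's conclusions.

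**What to change.** Reword the one sentence in section 9. Either make the trigger the decision uncertainty over the model horizon to age 18, or drop the condition and calculate the EVSI whatever the age-11 result. In both cases say that the EVSI is evaluated on the age-18 horizon, and report it next to the age-11 and age-18 acceptability results. If the looser meaning of the condition was intended, the same rewording makes that plain.

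The cost is the edit and at most one additional EVSI calculation on the probabilistic model already planned. The downside is that the result may prove near zero. Dropping the condition is the simpler option, because the EVSI itself falls to about zero when the age-18 decision is not in doubt.
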